These studies demonstrate that, perhaps surprisingly, symbolic conditioning or suggestion-based manipulations affect pain perception more than experience-based conditioning. There are, however, a few properties that are common to the above described studies. In these previous studies: (1) there was only one session with a limited number of trials (for example, 10 test trials without extinction for the symbolic conditioned cues in Jepma et al., 2018 ⁴ and 24 conditioning trials per cue, out of which only half were in fact low/high in accordance with the preceding cue rather than an identical moderately intense stimulus, in Koban et al., 2016 ⁸); (2) the difference between low and high pain stimuli was somewhat ambiguous, as the stimuli were relatively short (1 second at peak temperature) and the difference between low and high intensity was 1-2°C; and (3) in some of them, conditioned cues were combined with social cues. The social cues may have interfered learning of the cue-intensity pairing ^{5,8}. Overall, it is likely that the effect of conceptual conditioning and suggestions will eventually be extinct, and that experience-based conditioning will affect pain perception of all or most participants, across many trials or sessions, or when the low/high heat stimuli are more distinctive.

Another factor that has been shown to affect pain perception is the context. For example, an identical moderate heat stimulus was perceived as less painful (based on pain reports, SCRs and brain responses) when it was the better ("relative relief context", the other alternative was high heat) compared to the worst ("control context", the other alternative was low heat) option ^{7,10}. However, the results of these studies can be explained by the positive/negative affective response evoked by the visual representation of the outcome before heat onset, also presumably affecting expectations. Therefore, it is interesting to test whether the

counterfactual option affects pain perception when the outcome is not presented beforehand, and also when the alternatives are qualitatively, not just quantitatively, different.

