For each participant, each cue will be paired with a distribution of low or a distribution of high heat stimuli in one of three ways: pure instructions, symbolic learning and/or experience-based conditioning. We will then test how each of these pairing methods affect anticipatory and pain responses across time following the different cues. We will also include an additional neutral cue that will not be paired with any intensity, to serve as a baseline condition. The "cue-pain conditioning" component will include the four following tasks:

[figure not shown]
 Symbolic learning: This task will be similar to previous studies in our lab ^{4,9}. Low/high cues will be paired with pictures of thermometers showing low/high temperatures, respectively, without pain delivery. These cues will not be predictive of actual intensity in the following tasks that will include heat stimuli.

- 2) *Conditioning*: Low/high cues will be paired with heat stimuli taken from low/high intensity distributions, respectively, without suggestion. These cues will be predictive of actual intensity in the conditioning task, but not in the test task (see below).
- 3) *Test*: All cues will be presented in this task in a pseudo-random order and will be proceeded by heat stimuli with moderate intensity. This will allow us to compare the effect of the different cues on expectations and pain responses evoked by the same moderate stimuli. More than one moderate temperature will be used in the test task, to ensure that heat intensity affects pain responses, and pain reports are not driven by demand characteristic.
- 4) *Cues recognition*: In this task, all cues will be randomly presented one by one and participants will be asked to rate how hot they expect the stimulus paired with this cue to be. This task will be used to test explicit learning, in addition to the expectation ratings during the test task.

In the pure instructions condition, participants will be instructed for each cue whether it is paired with low or with high heat stimuli, without further conditioning. These cues will not be predictive of actual intensity in the following tasks.

In order to control for order effects between the symbolic learning and conditioning tasks, their order will be counter-balanced across sessions and participants (see below).

The structure of the tasks across the 10 sessions will be as follow (the order of the symbolic learning and conditioning tasks will change between participants):

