N-of-few Study of Pain Perception (NOF)

NCT04664400

Statistical Analysis Plan

8/3/22

Statistical analysis plan

Our main statistical analysis will be focused on participants' pain ratings following high vs. low cues for each of the conditions (symbolic learning, conditioning, and instructions only). For each condition, we will report the mean and standard deviation across participants test for significant differences in pain ratings following low vs. high cues with paired t tests, using statistical threshold of alpha = 0.05.

For the counterfactual task, we will compare ratings of the same pain stimulus when it is the better vs. the worst alternative, reporting the mean and SD across participants for this difference, and testing for significance with a paired t test.

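### The SAP tests the cue effect separately in each condition and plans no estimate or test of the difference between conditions, although the protocol's background predicts such a difference

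*SAP*

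**What the plan says.** The SAP's main analysis takes pain ratings after high and low cues in three conditions: symbolic learning, conditioning and instructions only. It states: "For each condition, we will report the mean and standard deviation across participants", and will "test for significant differences in pain ratings following low vs. high cues with paired t tests", "using statistical threshold of alpha = 0.05". Its only other test concerns the counterfactual task. It has no cue-by-condition term, no difference of differences and no interval for a between-condition difference. Protocol section 4 (Analysis) lists broad classes of method, including regression and Bayesian models, but names no contrast.

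The protocol sets up a comparison in three places.

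- Section 1 (Introduction and Background) reads earlier work as showing that "symbolic conditioning or suggestion-based manipulations affect pain perception more than experience-based conditioning". It then expects the reverse over many trials or sessions: suggestion effects fading out, and conditioning working in all or most participants.
- Section 3 (Cue-pain conditioning, Test) presents all cues in one task: "This will allow us to compare the effect of the different cues on expectations and pain responses evoked by the same moderate stimuli".
- The same section counterbalances training: "In order to control for order effects between the symbolic learning and conditioning tasks, their order will be counter-balanced across sessions and participants".

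Section 3 also provides a neutral cue: "We will also include an additional neutral cue that will not be paired with any intensity, to serve as a baseline condition". The SAP does not use it.

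**The concern.** A significant result in one condition and a non-significant result in another is not evidence that the two differ. With 5 to 10 participants, chance alone will often produce that pattern when the true effects are equal. The background invites the reader to ask whether conditioning now outperforms suggestion. The three separate tests are the only planned inference that bears on this, so a report that follows the SAP would have no valid basis for an answer in either direction. What is at stake is an unsupported statement that one pairing method works and another does not, or the loss of a contrast that the design can estimate.

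**Working it through.** **Inputs from the documents.** N is 5 to 10 (protocol section 9a), with 10 hoped for (section 3, COVID-19 procedures). Alpha is 0.05 (SAP). There is one paired t test per condition. The plan has no power calculation to reproduce.

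**Assumptions, because the documents give no figures.** Tests are two-sided. Let dz be the mean high-minus-low difference divided by its SD across participants. I take dz from 0.5 to 1.5, equal SDs in all conditions, and correlation ρ of 0 or 0.5 between conditions, since the same people supply all of them.

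**Step 1: power of one within-condition test.** Power = P(|T| > t₀.₉₇₅,ₙ₋₁), where T is noncentral t with n−1 df and noncentrality dz√n. At dz = 1.0:

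- N = 10: critical value 2.262, noncentrality 3.162, power p = 0.803.
- N = 5: critical value 2.776, noncentrality 2.236, power p = 0.401.

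**Step 2: chance that two equally effective conditions get different verdicts.** At ρ = 0 this is 2p(1−p). For dz = 1.0 that is 2 × 0.803 × 0.197 = 32% at N = 10 and 2 × 0.401 × 0.599 = 48% at N = 5. Values at ρ = 0.5 are from simulation (200,000 runs).

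| dz | N = 5, ρ = 0 | N = 5, ρ = 0.5 | N = 10, ρ = 0 | N = 10, ρ = 0.5 |
|---|---|---|---|---|
| 0.5 | 24% | 20% | 41% | 30% |
| 0.8 | 40% | 31% | 47% | 34% |
| 1.0 | 48% | 37% | 32% | 24% |
| 1.5 | 41% | 32% | 2.5% | 2% |

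When two equal conditions disagree in this way, a direct test of their difference is itself significant in only about 6% to 19% of cases.

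**Step 3: what a direct contrast would do.** Take conditioning minus the mean of the other two, with unit SD per condition. Its variance is 1 + ¼(2 + 2ρ) − 2ρ = 1.5(1 − ρ), so its SD is 1.225 at ρ = 0 and 0.866 at ρ = 0.5. A true difference of 1 SD is then a standardised effect of 1/1.225 = 0.816 or 1/0.866 = 1.155. A difference of 0.5 SD gives half of each.

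| True difference | N = 5 (ρ = 0 to 0.5) | N = 10 (ρ = 0 to 0.5) |
|---|---|---|
| 1 SD | 29% to 50% | 63% to 90% |
| 0.5 SD | 11% to 17% | 21% to 37% |

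If the true effects are equal, one such contrast rejects 5% of the time. If symbolic minus instructions is also tested at 0.05, the chance of at least one false positive is about 1 − 0.95² = 9.8%, and simulation gives the same.

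**The case against.** The strongest reply is that the comparison is not a stated aim. No numbered objective asks for conditioning versus suggestion: objectives 2 and 3 treat them separately. The stronger effects hypothesised for conditioning in objective 3 read most naturally as stronger than in earlier studies. The sentence ranking suggestion above conditioning summarises past work. Comparing the effects of different cues can also be met by high versus low within a condition. All of this stands. A reader might infer that a declared between-condition objective has been left without an analysis, and the documents do not support that. What remains is the background's expectation of opposite courses for the two kinds of pairing, tested on common stimuli with training order counterbalanced. Training order is more likely to disturb a comparison between methods than a high-low difference within one, though the protocol does not say this.

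A reader might also infer that the SAP will rank conditions by which p-values fall below 0.05. It does not say so, and it reports a mean and SD per condition, which allow an informal comparison of size. They give no test or interval for the within-participant difference. The regression and Bayesian methods in protocol section 4 could hold such a contrast, but none is specified.

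Finally, at dz = 1.0 with independent errors, three equal conditions fail to agree in 47% of studies at N = 10 and 72% at N = 5. Those figures should not be taken as the size of the problem. They rest on one assumed effect and ignore the shared participants: at ρ = 0.5 they fall to 35% and 55%.

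**Conclusion.** The concern holds as a gap in the SAP, not as a planned error. The SAP gives no estimate or test of a contrast that the protocol's background raises and its design permits. With equal true effects of dz 0.5 to 1.0 and ρ of 0 to 0.5, two conditions would receive different verdicts in about 20% to 48% of studies at N = 5 and 24% to 47% at N = 10. With very large effects (dz 1.5) the problem nearly vanishes at N = 10 (2% to 3%) but not at N = 5 (32% to 41%). Effect sizes, equal SDs and correlations are my assumptions. The absence of the contrast is a matter of reading and does not depend on them.

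**What to change.** Add to the SAP:

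1. For each participant, compute the high-minus-low difference in each condition. Name one primary contrast, conditioning minus the mean of symbolic learning and instructions, with a paired t test and 95% CI. Report symbolic learning minus instructions as secondary, with a CI.
2. State which sessions enter, for example test sessions 7-10 after learning has ended, or add a session term. The predicted difference is one of change over time, and an average over all sessions cannot separate a fading effect from a uniformly smaller one.
3. State that any claim that methods differ will rest on this contrast only, and that it is mainly an estimate, given its power near N = 5.
4. Optionally, report high-minus-neutral and low-minus-neutral differences with CIs as description, to show whether high cues raise ratings or low cues lower them. No objective requires this.

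If no claim about the relative effect of the methods is intended, one sentence saying so would also close the gap.

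The cost is SAP wording and a few lines of analysis on ratings the protocol already plans to collect. The downside is one or two more contrasts, with about a 10% chance of at least one false positive if both are tested at 0.05; giving the second as an interval only avoids that. The documents do not show whether the ratings have been seen. If they have, the contrast should be labelled as added afterwards.
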